3.3.5.2 Procedures for discontinuation

Volunteers who discontinue should always be asked about the reason(s) for their discontinuation and the presence of any AEs. If possible, they should be seen and assessed by an Investigator. Adverse events should be followed up and investigational products should be returned by the volunteer.

If a volunteer is being withdrawn due to a suspected infection in World Health Organisation (WHO) risk categories 2, 3, and 4, no biological samples from this volunteer are allowed to be sent to the laboratory. Samples will be destroyed according to normal routines at the study site.

If a volunteer withdraws consent to continued study participation, it must be specifically determined whether or not they also withdraw consent to future analysis of their biological samples collected during the study (in this case, blood and urine samples for future biomarker analysis) as this may entail destruction of the volunteer's stored samples.

Samples that have already been used for the intended research cannot be destroyed, and the results obtained will continue to be used for their intended research purposes. If consent is withdrawn to further analysis of stored samples before the samples are analysed, these will be traced as quickly as possible, and destroyed, or returned to the study site if required by local regulations.

3.3.5.3 Procedures for handling incorrect enrolled subjects

Volunteers not meeting the inclusion/exclusion criteria for a study should, under no circumstances, be enrolled into that study - there can be no exceptions to this rule.

Where volunteers not meeting the study criteria are enrolled in error, incorrectly randomised, or where volunteers subsequently fail to meet the criteria for the study post enrolment, procedures to be followed for the discontinuation of such volunteers are given in Section 3.3.5.2.

3.3.5.4 Procedures for discontinuation from genetic aspects of the study

Volunteers who discontinue from the study should always be asked specifically whether they are withdrawing or continuing their consent for this linked genetic research. It must be established whether the volunteer:

- Agrees to the genetic sample and any deoxyribonucleic acid (DNA) extracted from the sample being kept for genetic analyses in the future.
- Withdraws consent for the sample to be kept for genetic analysis in the future and wishes the sample to be destroyed. Destruction of the sample (or the DNA extracted from the sample) will only be possible so long as the particular sample is

traceable. In the event that genetic research has already been performed, AstraZeneca will retain the results and associated data for regulatory reasons but these will not be used in any subsequent analyses.

The Principal Investigator is responsible for providing written notification to AstraZeneca of any volunteer who has withdrawn consent for the use of the sample taken for genetic research. AstraZeneca will provide written confirmation to the Investigator of the actions taken with the sample, which must be filed in the investigator study file.

Requests for sample destruction should be forwarded to the head of the Clinical Genotyping Group (CGG) at [REDACTED], UK. Requests should include copies of the relevant documentation detailing study protocol number and volunteer Ecode. The clinical study team and the Investigator will receive written confirmation from CGG that the sample has been destroyed.

3.4 Treatment(s)

3.4.1 Investigational product(s)

3.4.1.1 Identity of investigational product

AZD9668 will be provided as a tablet for oral administration and with a matching placebo. Tablets of AZD9668 will be provided in the strengths 10 mg and 30 mg (Table 5).

Table 5 Identity of investigational product

Investigational product	Dosage form and strength	Manufacturer	Formulation number	Batch number
AZD9668	Tablet 10 mg	AstraZeneca	1756-4	Will be detailed in the CSR
	Tablet 30 mg	R&D, [REDACTED] [REDACTED]	1756-1	
Placebo AZD9668	Tablet	AstraZeneca R&D, [REDACTED] [REDACTED]	P1756-0	Will be detailed in the CSR

The composition of the tablet is 10 mg and 30 mg AZD9668 (corresponding to 13.2 mg and 39.5 mg AZD9668 tosylate).

Excipients: cellulose microcrystalline, calcium hydrogen phosphate dihydrate, crospovidone, sodium laurilsulfate, sodium stearyl fumarate.

The drug product is a white to off-white, plain oblong, biconvex tablet. The different tablet strengths are size matched. The nominal tablet weight is 400 mg.

Placebo tablets match the AZD9668 tablets in appearance and contain the following excipients: cellulose microcrystalline and sodium stearyl fumarate.

3.4.1.2 Labelling

The investigational product will be supplied as bulk supply. Study site dispensary staff will dispense the investigational product according to the random scheme. Individual volunteer containers will be labelled with a detachable tear off label. The AZD9668, or matching placebo, tablets will be filled in high-density polyethylene (HDPE) bottles with a child restraint cap.

The packaging and labelling will be performed by Investigational Product Supplies (IPS), AstraZeneca R&D [REDACTED]. All supplies and labels will be prepared in accordance with Good Manufacturing Practice (GMP) and local regulatory guidelines. The labels will fulfil the GMP Annex 13 requirement for labelling.

Each dosing container will be labelled with a one-part detachable tear-off label, which will be affixed to the case report form (CRF) at the time of administration.

3.4.1.3 Storage

All investigational products must be kept in a secure place under appropriate storage conditions. A description of the appropriate storage and shipment conditions are specified on the investigational product container label and in the Investigator's Brochure. The storage location will be locked and only accessible to authorised site personnel.

3.4.1.4 Accountability

The medication provided for this study is for use only as directed in the protocol. All unused study drugs will be accounted for and destroyed appropriately by [REDACTED] personnel. The study personnel will account for all drugs dispensed and returned. Certificates of delivery and return must be signed.

The Investigator (or delegated staff) is responsible for maintaining study drug accountability at site.

3.4.2 Doses and treatment regimens

Tablets of AZD9668/placebo will be administered by the Investigator (or his qualified staff) on each dosing day. The study drug will be taken orally in an upright position with 240 mL of water and the volunteers must drink all the water.

Each volunteer will receive two ascending single doses (on Days 1 and 7) followed by multiple doses (twice daily each dose administered 12 hours apart) for 6 days (Days 13-18), and a final single dose on the morning of Day 19 (ie, a total of 15 doses).

The proposed single dose levels are 30 mg, 60 mg, 120 mg and 150 mg, although they may change with emerging data from this study. The top dose will be no higher than 150 mg as this is the maximum dose that was administered to healthy volunteers in the AstraZeneca Global SAD/MAD Study and was found to be safe. In addition, modelled PK data from the

current study will ensure that the predicted geometric mean C_{\max} and $AUC_{(0-24)}$ at the top dose will not exceed 2.5 μM or 18 $\mu\text{M}\cdot\text{h}$, respectively.

The multiple doses for both cohorts 1 and 2 will be selected following a safety review meetings using emerging data from the current study and the AstraZeneca Global SAD/MAD Study. The maximum multiple dose will be capped at a total daily dose of 140 mg. In addition, the emerging PK data from the current study will be modelled to ensure that for the highest dose given, the predicted geometric mean exposures (both $AUC_{(0-24),\text{ss}}$ and $C_{\max,\text{ss}}$) will not exceed 2.5 μM or 18 $\mu\text{M}\cdot\text{h}$, respectively.

Cohorts of Japanese and Caucasians healthy volunteers will receive the same dose of AZD9668, and will be run in parallel as far as is possible.

For the single doses, volunteers will be fasted from midnight the night before dosing day, except water for thirst. On waking on the morning of each dosing day volunteers will consume 150 mL of water. This must be a minimum of 1 hour before dosing. No further fluids will be allowed before dosing. Two hours post dose, volunteers will be provided with 200 mL of water. No food is allowed until 4 hours after dosing. Lunch will be served at approximately 4 hours post dose, and an evening meal between 8 and 10 hours post dose. From lunchtime onwards the volunteers will be allowed fluids and snacks within the restrictions of the study.

For the multiple doses, volunteers will be fasted from midnight the night before dosing day, except water for thirst. On waking on the morning of each dosing day volunteers will consume 150 mL of water. This must be a minimum of 1 hour before dosing. No further fluids will be allowed before dosing. On Days 13 and 19, the volunteers will be provided with 200 mL of water post dose and no food is allowed until 4 hours after dosing. Lunch will be served at approximately 4 hours post dose, and an evening meal between 8 and 10 hours post morning dose. Volunteers will not be allowed food or fluids for 2 hours before and 2 hours after their evening dose, after which they are allowed free access to fluids and snacks within the restrictions of the study up to midnight (when they will fast for their next day's dose). On Days 14–18, volunteers will have the same restrictions except that they will be allowed a light breakfast at 2 hours post morning dose.

3.4.3 Method of assigning subjects to treatment groups

Informed consent will be obtained before enrolment and the volunteers identified with an enrolment number starting with E0001001. Numbers will be allocated in ascending order.

Volunteers fulfilling the eligibility criteria will be assigned randomisation codes (unique volunteer numbers), starting with 100 (Japanese volunteers) and 200 (Caucasian volunteers). Numbers will be allocated in ascending order.

Volunteers will be assigned randomisation codes strictly sequentially as volunteers are eligible for randomisation. If a volunteer discontinues from the study the volunteer number will not be re-used and the volunteer will not be allowed to re-enter the study.

The randomisation schedule and associated individual treatment code envelopes (emergency unblinding tools) giving details of individual volunteer treatment will be produced by computer software (SAS[®]) that incorporates a standard procedure from generating randomisation codes.

Both Japanese and Caucasian volunteers will be allocated to either AZD9668 or placebo in a 6:2 ratio (AZD9668:placebo) per cohort. At each dose level, Japanese and Caucasian volunteers will be gender and age matched (± 5 years).

3.4.4 Blinding and procedures for unblinding the study

3.4.4.1 Methods for ensuring blinding

AZD9668 and placebo tablets are manufactured to appear similar in size, shape, weight and colour.

3.4.4.2 Methods for unblinding the study

Individual treatment codes, indicating the treatment randomisation for each randomised volunteer, will be available to the Investigator at the study centre and the personnel who are independent of the study evaluation at the Drug Safety Department, AstraZeneca [REDACTED].

The individual treatment codes must not be broken except in medical emergencies when the appropriate management of the volunteer necessitates knowledge of the treatment randomisation. The Investigator must document and report to AstraZeneca any breaking of the treatment code. AstraZeneca retains the right to break the code for SAEs suspected to be causally related to an investigational product and that potentially require expedited reporting to regulatory authorities.

Treatment codes will not be broken for the planned analyses of data until all decisions on the evaluability of the data from each individual volunteer have been made and documented.

The following personnel will have access to the randomisation list:

- The personnel carrying out packaging and labelling of investigational product.
- The personnel dispensing the investigational product at the [REDACTED]
- The personnel analysing the PK samples.

The information in the randomisation list must be kept in a secure location until the end of the study.

3.4.5 Concomitant medication

No concomitant medication or therapy will be allowed except paracetamol (1 g, a minimum of 4 hours between doses, up to a maximum daily dose of 4 g) for occasional use and HRT. The volunteers must be instructed that no additional medication will be allowed without the prior consent of the Investigator, although this does not preclude emergency treatment. In this

situation the medication/treatment received must be reported to the Investigator as soon as possible.

Any medication, which is considered necessary for the volunteer's safety and well-being, may be given at the discretion of the Investigator. The administration of all medication (including investigational products) must be recorded in the appropriate sections of the CRF.

3.4.6 Treatment compliance

Compliance will be assured by supervised administration of the investigational product by the Investigator or delegate.

4. MEASUREMENT OF STUDY VARIABLES

The following study measurements will be obtained. The timing of these measurements is detailed in the study plan (Table 1). All assessments will be performed at the scheduled timepoints (pre dose ± 30 minutes; post dose ± 10 minutes). The following 'priority order' will be in effect when more than one assessment is required at a particular time point:

ECG; vital signs (blood pressure and pulse); PK sample; PD sample; safety blood samples.

4.1 Medical examination and demographic measurements

4.1.1 Enrolment medical examination and demographic measurements

Volunteers will attend the [REDACTED] to provide written informed consent at Visit 1a. Subsequently, each eligible volunteer will undergo an enrolment medical examination at Visit 1b (up to 21 days prior to Visit 2). Volunteers should be fasted (minimum of 8 hours), with only water permitted.

Assessment at Visit 1b will include:

- Recording of demographic data - date of birth, sex, ethnic origin, BMI, smoking status (ie, number of cigarettes/cigars/etc smoked per day).
- A standard medical and surgical history assessment and review.
- Concomitant medication assessment and review.
- Physical examination (including height and weight).
- An alcohol screen (breath test).
- Virology blood sample for Hepatitis B surface antigen, Hepatitis C antibody, and HIV status.
- A 12-lead ECG (paper).

- Resting blood pressure and pulse measurement (sitting position).
- A blood sample (fasted) for standard clinical chemistry (including FSH at Visit 1b for female volunteers) and haematology assessments, and a mid-stream urine sample for urinalysis and drugs of abuse screen.
- Pregnancy test (female volunteers only).

4.1.2 Post-study medical examination (Visit 5)

Procedures at the follow-up visit (Visit 5) will consist of:

- Concomitant medication assessment and review.
- Physical examination (weight only will be measured at this visit).
- An alcohol screen (breath test).
- A 12-lead ECG (paper).
- Resting blood pressure and pulse measurement (sitting position).
- A blood sample for standard clinical chemistry and haematology assessments, and a mid-stream urine sample for urinalysis and drugs of abuse screen (only required if volunteer was allowed out of the clinical unit during the study).
- Assessment of AEs.

4.2 Pharmacokinetic measurements

For timing of individual samples refer to the study plan (Table 1).

The number and timings of PK sample collection may be revised based upon emerging data from the AstraZeneca Global SAD/MAD Study, but the total number of samples will not be increased from those listed in Table 3.

4.2.1 Determination of drug concentration in biological samples

Plasma samples for measurement of drug concentration will be analysed by Plasma samples for measurement of drug concentration will be analysed by [REDACTED] AstraZeneca R&D [REDACTED] using a validated method of liquid chromatography and mass spectrometry (LC-MS/MS). The lower limit of quantification (LLOQ) will be 1.00 nM.

Urine samples for the determination of AZD9668 concentrations will be analysed using appropriate quantitative methods (including test of stability) by Plasma samples for measurement of drug concentration will be analysed by [REDACTED] AstraZeneca R&D [REDACTED]. The methods used will be referred to in the CSR.

Both plasma and urine samples may be used in exploratory metabolite identification investigations, which in such case will be reported separately.

4.2.2 Collection of biological samples

4.2.2.1 Blood samples for PK measurements

Blood samples (4 mL K₂EDTA) for determination of AZD9668 in plasma will be taken at the times presented in Table 3.

Blood samples will be collected, labelled and shipped as detailed in the laboratory handbook. The date and time of collection will be recorded on the appropriate CRF page.

Samples should be stored at -18°C or below, and analysed within the timeframe after collection for which the stability in the samples has been validated and found acceptable. Results from analyses stored longer than the period stated will not be reported.

The methods used will be referred to in the CSR.

Samples may be kept for up to five years before destruction.

4.2.2.2 Urine samples for PK measurements

Urine will be passed into a specially provided container(s) at the times presented in the study plan (Table 1). Urine containers should be stored in the refrigerator (2-8°C) when not in use during the collection period. Samples will be collected, labelled and shipped as detailed in the laboratory handbook.

The date and time of collection will be recorded on the appropriate CRF page.

After mixing, 4 x 10 mL aliquots will be removed into polypropylene tubes (only 2 x 10 mL aliquots will be removed for the “blank” when the volunteers empty their bladders prior to dosing). Samples should be stored at -18°C or below.

The methods used will be referred to in the CSR.

Samples may be kept for up to five years before destruction.

4.3 Pharmacodynamic measurements

4.3.1 Ex-vivo zymosan stimulated neutrophil elastase (NE) activity in plasma

A blood sample (4.5 mL sodium citrate vacutainer) will be taken for the analysis of zymosan stimulated NE activity at times indicated in Table 4.

Each blood sample will be aliquoted as follows:

Pre-dose samples

- (a) Unstimulated.

- (b) Zymosan stimulated.
- (c) Zymosan stimulated and single concentration of AZD9668 (AZD9668 will be added *ex-vivo* to act as a positive control).

Post-dose samples

- (a) Unstimulated.
- (b) Zymosan stimulated.

All samples will be incubated at 37°C and handled according to instructions in the laboratory handbook. Following incubation, the samples will be processed and separated before freezing. Samples should be frozen at -18°C or below and transferred frozen, on dry ice, to [REDACTED] AstraZeneca R&D, [REDACTED] for analysis.

The number and timings of sample collection may be revised based upon emerging data from the AstraZeneca Global SAD/MAD Study, however the total number of samples will not be increased from those listed.

Samples may be kept for up to five years before destruction.

Full details of sample processing and shipping can be found in the laboratory handbook.

4.3.2 Method of assessment

Plasma aliquots are analysed for NE activity in a 96-well assay format using a fluorogenic substrate that is cleaved according to NE activity. Increasing activity yields increasing amounts of the cleavage product 7-amino 4-methyl coumarin (AMC).

4.4 Safety measurements

4.4.1 Laboratory safety measurements

Blood and urine samples for the determination of clinical chemistry, haematology and urinalysis parameters will be taken at the times given in the study plan (Table 1). The date of collection will be recorded on the appropriate CRF page.

Samples will be collected in the following tubes and at the volumes specified:

Clinical chemistry – 8.5 mL serum separation tube (SST) vacutainer.

Haematology – 3 mL EDTA vacutainer.

Urinalysis – 20 mL universal tube.

The following laboratory variables will be measured:

Clinical Chemistry

Creatinine	Triglycerides
Total, conjugated, and unconjugated bilirubin	Urea
Alkaline phosphatase	Gamma Glutamyltransferase (GGT)
Aspartate aminotransferase (AST)	Creatinine phosphokinase (CPK) ^a
Alanine aminotransferase (ALT)	Lactate dehydrogenase (LDH)
Albumin	Glucose (fasting)
Potassium	Follicle stimulating hormone (FSH) ^c
Calcium, total	Haptoglobin
Sodium	
High sensitivity C-reactive protein (hsCRP)	
Cholesterol	

Haematology

Haemoglobin
Leukocyte count
Red cell count (RBC)
Haematocrit
Mean cell volume (MCV)
Mean cell haemoglobin (MCH)
Mean cell haemoglobin concentration (MCHC)
Leukocyte differential count (absolute)
Platelet count
Reticulocyte count

Urinalysis

Blood
Protein
Ketones
Glucose
Bilirubin
Urobilinogen

Virology ^b

Hepatitis B surface antigen
Hepatitis C antibodies
HIV 1 and 2 antibodies

^a If elevated >3, P-CPK-MB will be analysed (will not be data-based).

^b Included at Visit 1b only.

^c Only analysed in female volunteers. Included at Visit 1b only.

Urine will be tested for the following drugs of abuse:

Methadone, benzodiazepines, cocaine, amphetamines, tetrahydrocannabinoids (THC), morphine, methamphetamines (ecstasy), barbiturates, phencyclidine (PCP) and tricyclic antidepressants (TCA).

If a volunteer tests positive for drugs of abuse they will be excluded from entering, or continuing in, the study.

Female volunteers must give a sample of the first urine passed at Visit 1b for a pregnancy test to be performed. It is important to check that volunteers are not pregnant when they enter the study but it is unnecessary to re-test during the study as they have already been defined as 'non-childbearing potential'.

4.4.2 Electrocardiographic measurements

For timing of individual measurements refer to study plan (Table 1).

4.4.2.1 Resting 12-lead ECG

Paper ECG

Paper ECGs will be recorded prior to each dECG recording (see Table 2), and at 48 and 72 hours post dose at Visits 2, 3 and 4.

Prior to the acquisition of the 12-lead ECG at each timepoint, the volunteer must be rested in bed for at least 10 minutes. The volunteer must be in the same supine (maximum 30 degrees flexion in the hip) body position at each time point at all visit and feet not in contact with footboard. The skin must be cleaned, and electrode positions marked with an indelible pen. Electrodes should be applied 30 minutes before first recording.

Digital ECG (dECG)

If required*, dECGs will be recorded for three 10-second intervals over two minutes at the timepoints (shown in Table 2) at Visits 2 and 3 (single doses) and after the first and last multiple doses (ie, on Days 13 and 19 [Visit 4]).

* The need to perform dECGs will be based on the outcome of the ongoing AstraZeneca Global SAD/MAD Study.

The same recorder will be used for each volunteer during all study visits, if possible. Date and time settings must be checked at the start of the study day and aligned with an official timekeeper for all machines used in the study.

Upon completion of ECG recordings for each dose panel, the digital files are transferred from the ECG machines to an external company for over-reading by an independent cardiologist. The cardiologist will perform the analysis in a blinded manner. Each ECG will be faxed back to the site within 48 hours with the cardiologist's signature and date of review. The cardiologist will contact the site by telephone if there are any findings of concern. Beside the final analysis, at agreed dates, safety evaluation of the dECG data will be submitted to the SRC for evaluation before dose escalation.

In this study lead V2 will be analysed and reported as primary. Lead V5 will be analysed, for all visits, as backup for the individual where analysis in lead V2 is not deemed possible for

pre-dose or significant parts of whole visits or whole visits. The following variables will be reported: RR, PR (PQ), QRS, QTang, QTcB, QTcF and QTcX will be calculated.

Additional safety paper ECGs are to be taken before each dECG recording and at the discretion of the Investigator for safety reasons. The QTc is calculated automatically by the Marquette MAC 1200 (General Electric Healthcare, UK) according to Bazett's formula and the QT time is the same in all leads of the averaged complex. These paper ECGs will be reviewed by the Investigator and evaluated in his opinion, as "Normal" or Abnormal" or "Not Clinically Significant" (NCS) and stored with the CRF. If the QTc is considered prolonged, a repeat paper ECG and a dECG should be recorded within 30 minutes.

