⁷ Telemetry from -1 to 24 hrs post-dose at Visits 2, 3 and 4, and from -1 to 24 hrs post dose on Day 19 (Visit 4).

⁸ Vital signs will be measured at the timepoints shown in Table 2.

⁹ Female volunteers only.

¹⁰ PK sampling times are detailed in Table 3.

¹¹ Urine collections: Pre-dose on Days 1, 7 and 13 and post dose at 0-4, 4-8, 8-12, 12-24, 24-36, 36-48 hrs on Days 1, 7 and 19. On Day 13 at 0-4, 4-8, 8-12 hrs post dose.

¹² Pharmacodynamic (PD) blood sampling times are shown in Table 4.

¹³ Pharmacogenetic (PGx) blood sample to be obtained at any suitable timepoint post dose.

Table 2 ECG and vital signs assessment schedule – Visits 2, 3 and 4

Time (Relative to dosing)
-01:00
00:00
00:30
01:00
01:30
02:00
03:00
04:00
06:00
08:00
12:00
24:00

Paper ECGs, dECGs (if required), and vital signs (ie, sitting blood pressure and pulse) will be performed at the above times at Visits 2 and 3 (single doses) and after the first and last multiple doses (ie on Days 13 and 19 [Visit 4]). Paper ECGs will also be measured at 48 and 72 hours post dose at Visits 2, 3 and 4.

Table 3 Pharmacokinetic sampling schedule

Day	Time (hours - relative to dosing)
1	Pre-dose, 0.25, 0.5, 1, 2, 3, 4, 5, 7, 9, 12, 24, 36, 48, 72 post-dose
7	Pre-dose, 0.25, 0.5, 1, 2, 3, 4, 5, 7, 9, 12, 24, 36, 48, 72 post-dose
13	Pre-dose, 0.25, 0.5, 1, 2, 3, 4, 5, 7, 9, 12 (pre-dose 2), 13, 15 post-dose
14 and 15	Pre-dose (dose 1)
16 and 17	Pre-dose (dose 1), 1 post-dose
18	Pre-dose (dose 1)
19	Pre-dose, 0.25, 0.5, 1, 2, 3, 4, 5, 7, 9, 12, 24, 36, 48, 72 post-dose

Table 4 Pharmacodynamic sampling schedule

Day	Time (hours - relative to dosing)	
	Cohort 1	Cohort 2
1	Pre-dose, 1, 24 post-dose	Pre-dose, 1, 48 post-dose
7	Pre-dose, 1, 48 post-dose	Pre-dose, 1, 48 post-dose
13	Pre-dose (dose 1), 1 post-dose	Pre-dose (dose 1), 1 post-dose

Time (hours - relative to dosing)		
19	Pre-dose, 1, 24 post-dose	Pre-dose, 1, 48 post-dose

Total of 11 blood samples per volunteer in each cohort.

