3.1.1.2 Stopping criteria for dose escalation during the single dose phase

Escalation to the next dose level will not occur if any of the following criteria are met with the previous dose levels:

- Either an alanine aminotransferase (ALT) / aspartate aminotransferase (AST) level ≥ 3 x upper limit of normal (ULN) at two consecutive time points, or any pattern of liver function test (LFT) abnormalities giving cause for concern, in two or more volunteers on active treatment.

- Evidence of haemolysis as evidenced by the following in two or more volunteers on active treatment.
 - Reticulocyte count of over 5%, and,

At least two of the following:

- A drop in haemoglobin below 10.5 g/dL.
 - Decrease of 25% in haptoglobin. (The value post-dose to be compared with the average of two pre-dose values. The value should also be 15% below the lower limit of normal [LLN]).
 - Increase of 25% in unconjugated bilirubin or lactate dehydrogenase (LDH). (The value post-dose to be compared with the average of two pre-dose values. The value should also be 15% above ULN).
- A platelet count of below $80,000 \times 10^9/L$ confirmed by a repeat test (in the absence of obvious platelet clumping in a peripheral blood film) in two or more volunteers on active treatment.
 - A QTcF >500 ms in two or more volunteers on active substance (QT interval corrected for heart rate by Fridericia method) or a QTcF prolongation >60 ms on average, sustained for more than 30 minutes, ie, present on two contiguous timepoints, in two or more volunteers on active substance based on the results of the continuous readings compared to baseline.
 - Any general safety finding that in the opinion of the Investigator gives cause for concern.
 - Data indicate that at the next proposed dose, the geometric mean plasma C_{max} would be expected to exceed $2.5 \mu M$ or the geometric mean $AUC_{(0-24)}$ would be expected to exceed $18 \mu M.h$. If $AUC_{(0-24)}$ cannot be calculated $AUC_{(0-t)}$ will be used.

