3.1.1.3 Stopping criteria for dose escalation during the multiple dose phase

Escalation to the next dose level will not occur if any of the following criteria are met with the previous dose levels:

- Two or more volunteers on active treatment are discontinued because of either an ALT/AST level $\geq 3 \times ULN$ or any pattern of LFT abnormalities giving cause for concern.
- Evidence of haemolysis as evidenced by the following in two or more volunteers on active treatment.
 - Reticulocyte count of over 5%, and,

At least two of the following:

- A drop in haemoglobin below 10.5 g/dL.
 - Decrease of 25% in haptoglobin. (The value post-dose to be compared with the average of two pre-dose values. The value should also be 15% below LLN).
 - Increase of 25% in unconjugated bilirubin or LDH. (The value post-dose to be compared with the average of two pre-dose values. The value should also be 15% above ULN).
- A platelet count of below $80,000 \times 10^9/L$ confirmed by a repeat test (in the absence of obvious platelet clumping in a peripheral blood film) in two or more volunteers on active treatment.
 - A QTcF >500 ms in two or more volunteers on active substance (QT interval corrected for heart rate by Fridericia method) or a QTcF prolongation >60 ms on average, sustained for more than 30 minutes, ie, present on two contiguous timepoints, in two or more volunteers on active substance based on the results of the continuous readings compared to baseline.
 - Any general safety finding that in the opinion of the Investigator gives cause for concern.
 - Data indicate that at the next proposed dose the geometric mean steady state exposure ($C_{\max,ss}$ or $AUC_{(0-24),ss}$) will exceed 18 $\mu M.h$ and 2.5 μM , respectively.

Dosing in an individual volunteer may be discontinued in the multiple dose phase of the study (see Section 3.3.5.1 for criteria).

The stopping criteria refer to all volunteers at a specific dose level. In the event of the need to unblind the data for a given volunteer, or a given cohort, the study design will revert to a single blind study for that volunteer or cohort.

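### The cardiac stopping criteria need QTcF, which is planned only from conditional digital ECGs; the certain paper ECG reports Bazett QTc, and its fallback trigger can miss the >60 ms limb

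*Protocol*

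**What the plan says.** **The criteria.** Protocol Sections 3.1.1.2 (single dose escalation), 3.1.1.3 (multiple dose escalation) and 3.3.5.1 (discontinuation during multiple dosing) repeat the same two limbs. One is absolute: "A QTcF >500 ms in two or more volunteers on active substance". The other is a change: "QTcF prolongation >60 ms on average, sustained for more than 30 minutes, ie, present on two contiguous timepoints", again in at least two volunteers on active drug. The correction is explicit: "QT interval corrected for heart rate by Fridericia method". The source is given only as "based on the results of the continuous readings compared to baseline", with no device named.

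**Digital ECG.** Section 4.4.2.1 lists QTcF among the variables reported from the digital ECG, and nowhere else is it planned as a derived variable. Digital ECG data are also the only ECG data expressly sent to the Safety Review Committee before escalation. Whether these recordings happen is open: "The need to perform dECGs will be based on the outcome of the ongoing AstraZeneca Global SAD/MAD Study".

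**Paper ECG.** Under Table 2 in Section 3.1: "Paper ECGs, dECGs (if required), and vital signs (ie, sitting blood pressure and pulse) will be performed at the above times". Paper recordings are therefore unconditional, with further ones at 48 and 72 hours. On the correction, Section 4.4.2.1 says: "The QTc is calculated automatically by the Marquette MAC 1200 (General Electric Healthcare, UK) according to" Bazett's formula. The investigator grades each tracing and files it with the CRF.

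**Fallback.** "If the QTc is considered prolonged, a repeat paper ECG and a dECG should be recorded within 30 minutes" (Section 4.4.2.1). No figure defines prolonged.

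**Telemetry.** Section 4.4.2.2 provides 24-hour ambulatory monitoring with review and a signed printout. It mentions no QT measurement.

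**The concern.** The rule is written on one quantity and the recording sure to exist reports another. If the ongoing global study leads the sponsor to omit scheduled digital ECGs, nothing in the Protocol produces the QTcF values that the criteria require, and nothing produces a pre-dose QTcF to measure a change from. The fallback digital ECG does not close the gap. It is prompted by the Bazett value, by judgement, on a single tracing. A digital ECG first taken after prolongation is suspected also has no pre-dose counterpart.

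What is at stake is a safety rule applied during the study by the investigator and the committee, not a detail of the later analysis. Sections 1.1 and 3.2.2 name QT prolongation in the dog as one of the few preclinical findings of possible relevance to humans.

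**Working it through.** The plan gives no figure to reproduce. The check is formula arithmetic on the two corrections.

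**Inputs from the Protocol:** limits of QTcF >500 ms and a rise >60 ms (Sections 3.1.1.2, 3.1.1.3, 3.3.5.1); Bazett on the paper ECG (Section 4.4.2.1); QTc <450 ms as a normal ECG at screening, correction not named (Section 3.3.2, criterion 7).

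**Assumptions:** heart rates, which the Protocol does not give; and 450 ms as the meaning of prolonged, because it is the document's only numerical QTc limit for a normal ECG. Recordings are supine after at least 10 minutes' rest, so slow rates are plausible.

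**Formulas.** With RR = 60/HR in seconds, QTcB = QT/RR^(1/2) and QTcF = QT/RR^(1/3). Hence QTcB = k × QTcF, where k = RR^(-1/6). Below 60 bpm k is less than 1 and Bazett reads lower than Fridericia; above 60 bpm the reverse holds.

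**Change limb, constant rate.** Take a rise of 61 ms, which exceeds the limit.

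- At 50 bpm, k = 1.2^(-1/6) = 0.9701. QTcF 400 to 461 ms prints as 400 × 0.9701 = 388 to 461 × 0.9701 = 447 ms: below 450, no trigger.
- At 60 bpm, k = 1. QTcF 380 to 441 ms prints as 380 to 441 ms: also no trigger, although the two corrections agree.

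More generally, a 61 ms rise goes unseen whenever the baseline QTcF is below 450/k − 61:

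| HR (bpm) | k | QTcF at which QTcB = 450 (ms) | Rise of 61 ms missed if baseline QTcF is below (ms) |
|---|---|---|---|
| 45 | 0.9532 | 472.1 | 411.1 |
| 50 | 0.9701 | 463.9 | 402.9 |
| 60 | 1.0000 | 450.0 | 389.0 |
| 70 | 1.0260 | 438.6 | 377.6 |
| 80 | 1.0491 | 428.9 | 367.9 |

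The misses arise first because the trigger ignores change from baseline. Bazett at slow rates widens them: by 402.9 − 389.0 = 13.9 ms of baseline at 50 bpm compared with 60 bpm.

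**Change limb, falling rate.** If the rate drops from 65 to 50 bpm, QTcF 400 to 461 ms prints as 405.4 to 447.2 ms, a rise of 41.8 ms instead of 61.

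**Absolute limb.** A QTcF of 500 ms prints below a trigger T only when HR < 60 × (T/500)^6:

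- T = 450: 31.9 bpm
- T = 480: 47.0 bpm
- T = 500: 60 bpm

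**The case against.** Three replies deserve weight.

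First, telemetry is also certain to be done and is the only continuous recording, so it may be what the criteria mean. It may, but Section 4.4.2.2 derives no QT or RR from it, and a test on two contiguous timepoints suits scheduled tracings better than a continuous record. The source is unspecified.

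Second, a reader might infer that the rule would have no data at all. The documents do not support that. The paper ECG yields a QT time and a Bazett QTc at every Table 2 time, so QTcF can be recovered, and Section 6.2.1 provides for ECG change from pre-dose Visit 2. What is missing is any statement that QTcF will be derived from these tracings. Section 6.2.1 names no correction, and Table 2 has two times at or before dosing.

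Third, a reader might infer that a volunteer above 500 ms would escape notice at a slow rate, because QTcF 500 ms prints as 485 ms at 50 bpm and 477 ms at 45 bpm. Both values lie well above 450 ms and would probably prompt the digital ECG. The stopping limit is not the referral trigger, and at a 450 ms trigger the miss needs a rate below about 32 bpm. Likewise, Bazett over-calling at faster rates leads at worst to a confirmatory recording. These replies stand. They do not touch the >60 ms limb.

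**Conclusion.** The concern holds as an inconsistency in safety monitoring that should be corrected. Without scheduled digital ECGs, the cardiac criteria have no planned QTcF series and no planned QTcF baseline, and the fallback cannot be relied on to detect the >60 ms limb. With 450 ms as the trigger and no change in heart rate, a 61 ms rise is missed for any baseline QTcF below 389 ms at 60 bpm or below about 403 ms at 50 bpm. The >500 ms limb is practically safe at that trigger and becomes exposed only if prolonged is read more leniently (below 47 bpm at 480 ms, below 60 bpm at 500 ms). The heart rates and the trigger value are assumptions. The mismatch between the sections is not, and it applies only if digital ECGs are not scheduled.

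**What to change.** Reconcile Protocol Sections 3.1.1.2, 3.1.1.3, 3.3.5.1, 4.4.2.1 and 4.4.2.2 so that together they name one recording, one QT correction and one baseline that feed the existing criteria, whether or not digital ECGs are performed. Say what the continuous readings are, and how the prompt for an unscheduled digital ECG relates to the change limb. The clinical limits are not in question here, and the choice belongs to the sponsor and the investigator.

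Data need not be an obstacle. QTcF follows from the QT and RR of each paper ECG as QT/RR^(1/3). If only QT and the printed Bazett value are at hand, RR = (QT/QTcB)^2, so QTcF = QT^(1/3) × QTcB^(2/3). The cost is wording and a formula applied to tracings already planned, with no extra recordings.
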